APPENDIX 2 – DATA COLLECTION

Baseline:

Sourced/Collected by Local Research Team in a clinic visit

- Date of baseline visit
- Participant demographics
 - Ethnicity
 - Biological sex
 - Index of Multiple Deprivation
- Perthes' disease at diagnosis
 - Affected hips (unilateral, bilateral)
 - Current disease stage by radiological status
 - Waldenström classification (0,1A,1B,2A,2B,3A,3B,4)
 - Documented stiffness (stiff, minimal/no stiffness)
 - Degree of deformity (collapse) (>50%, exactly 50%, <50% lateral pillar height)

Direct Participant Report (collected electronically)

- Patient assessment of function
 - o PROMIS Mobility CAT
- Pain
 - Wong-Baker FACES Pain Scale
- Quality of life
 - o CHU-9D
- Impact of the condition
 - o PROMIS Pediatric Family Relationships Questionnaire

Intervention

Surgery

Sourced/Collected by Local Research Team in post-operative period.

- Date of surgery
- Grade of surgeon performing the operation
- Operation type (Varus osteotomy, shelf osteotomy, Salter osteotomy, other redirectional acetabular osteotomy, soft tissue surgery)
- Core decompression performed? (Yes/No)
- Hip distraction performed? (Yes/No)
- Intra-operative complications
- Post-Operative Instructions (Spica/ cast Yes (Duration?)/ No)

Best practice therapy session

Sourced/Collected by Local Research Team in a clinic visit

- Date of session
- Name of physiotherapist delivering session
- Length of session (minutes)
- Content of session included:
 - Individually tailored advice? (Yes/No)
 - Review of walking aids? (Yes/No)
 - Walking aids given (yes/no, if yes what?)

- Reassurance? (Yes/No)
- Education about the condition? (Yes/No)
- Activity modification? (Yes/No)
- Exercise advice? (Yes/No)
- o Pain management information? (Yes/No)
- Goal setting (yes/no)
- What to do if they experience problems? (Yes/No)
 - Any option above if select 'no', will prompt 'Why?'

3 months post randomisation

Sourced/Collected by Local Research Team in a clinic visit / telephone call

Date

Direct Participant Report (collected electronically)

- Patient assessment of function
 - o PROMIS Mobility CAT
- Pain
 - o Wong-Baker FACES Pain Scale
- Quality of life
 - o CHU-9D
- Impact of the condition
 - o Resource use
 - Participation in Education
 - o PROMIS Pediatric Family Relationships Questionnaire

6 months post randomisation

Sourced/Collected by Local Research Team in a clinic visit / telephone call

Date

Direct Participant Report (collected electronically)

- Patient assessment of function
 - o PROMIS Mobility CAT
- Pain
 - Wong-Baker FACES Pain Scale
- Quality of life
 - o CHU-9D
- Impact of the condition
 - o Resource use
 - Complications
 - o Participation in Education
 - o PROMIS Pediatric Family Relationships Questionnaire

9 months post randomisation

Sourced/Collected by Local Research Team in a clinic visit / telephone call

Date

Direct Participant Report (collected electronically)

• Patient assessment of function

- o PROMIS Mobility CAT
- Pain
 - Wong-Baker FACES Pain Scale
- Quality of life
 - o CHU-9D
- Impact of the condition
 - o Resource use
 - o Participation in Education
 - o PROMIS Pediatric Family Relationships Questionnaire

12 months post randomisation

Sourced/Collected by Local Research Team in a clinic visit / telephone call

Date

Direct Participant Report (collected electronically)

- Patient assessment of function
 - o PROMIS Mobility CAT
- Pain
 - Wong-Baker FACES Pain Scale
- Quality of life
 - o CHU-9D
- Impact of the condition
 - o Resource use
 - Complications
 - o Participation in Education
 - o PROMIS Pediatric Family Relationships Questionnaire

18 months post randomisation

Sourced/Collected by Local Research Team in a clinic visit / telephone call

- Date
- Complications

Direct Participant Report (collected electronically)

- Patient assessment of function
 - o PROMIS Mobility CAT
- Pain
 - Wong-Baker FACES Pain Scale
- Quality of life
 - o CHU-9D
- Impact of the condition
 - o Resource use
 - Complications
 - Participation in Education
 - o PROMIS Pediatric Family Relationships Questionnaire

24 months post randomisation

Sourced/Collected by Local Research Team in a clinic visit / telephone call

Date

Direct Participant Report (collected electronically)

- Patient assessment of function
 - o PROMIS Mobility CAT
- Pain
 - Wong-Baker FACES Pain Scale
- Quality of life
 - o CHU-9D
- Impact of the condition
 - o Resource use
 - Participation in Education
 - o PROMIS Pediatric Family Relationships Questionnaire

30 months post randomisation

Sourced/Collected by Local Research Team in a clinic visit / telephone call

Date

Direct Participant Report (collected electronically)

- Patient assessment of function
 - o PROMIS Mobility CAT
- Pain
 - o Wong-Baker FACES Pain Scale
- Quality of life
 - o CHU-9D
- Impact of the condition
 - o Resource use
 - Participation in Education
 - o PROMIS Pediatric Family Relationships Questionnaire

36 months post randomisation

Sourced/Collected by Local Research Team in a clinic visit / telephone call

- Date
- Complications/SAE review
- All radiographic images collected as part of routine practice will be harvested and given to the study team. In particular, images taken pre-operatively, post-intervention and as close as possible to the 3 year post intervention date will be collated.

Direct Participant Report (collected electronically)

- Patient assessment of function
 - o PROMIS Mobility CAT
- Pain
 - o Wong-Baker FACES Pain Scale
- Quality of life
 - o CHU-9D
- Impact of the condition
 - o Resource use
 - Complications
 - o Participation in Education
 - o PROMIS Pediatric Family Relationships Questionnaire

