| To estimate cost- effectiveness, from the UK NHS and Personal Social Services perspective in both groups | Non validated resource use questionnaire and CHU-9D | Baseline (CHU-9D only), 6, 9, 12, 18, 24, 30 and 36 months post randomisation | Resource use from hospital and out of pocket expenditure from families. CHU-9D score | Case report Form (entered directly into the REDCap study database) |
| To quantify the degree of residual deformity (waldenstrom grade and Stulberg classification) | Measured from routinely collected images of the hip or pelvis harvested from the picture archiving system. | An image of the hip or pelvis harvested from the picture archiving system within a 6 month timeframe of the primary outcome (36 months). | Routinely collected images of the hip or pelvis harvested from the picture archiving system. | Medical notes |

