23.2 Sample Size/Power calculations

172 participants providing data on the PROMIS Mobility Score for children at three years post randomisation (86 in each group) will provide 90% power to detect a difference in means of 5, assuming the standard deviation (SD) is 10 using a two group t-test with a 5% (2-sided) significance level. This is inflated to 216 participants (108 per arm) to allow for 20% attrition.

Raw scores of the PROMIS are translated into standardised T-scores with a population mean of 50 and an SD of 10.

The minimum clinically important difference (MCID) of PROMIS paediatric measures is generally 3.0-5.0 [29,30].

We discussed with children and families the size of the difference they would require to justify surgery, over optimised non-surgical containment. Given that surgery is a considerable intervention in the lives of the child and their family (i.e., the anaesthetic, the pain and scar, admission to hospital, the frequency of the requirement for a second procedure to removal metalwork, along with the lengthy

duration of immobilisation and recovery), families believed that the effect sought should be at the upper range of the MCID. Other studies have similarly highlighted that patients often seek greater effect sizes to warrant bigger surgical interventions than the established MCID [31].

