23.3.2 Secondary outcome(s)

Continuous secondary outcomes measured over time (PROMIS Mobility over time, Wong-Baker Faces Pain Scale, CHU-9D and PROMIS Family Relationships) will be compared using a multi-level mixed effects linear regression model with repeated measures (level 1) grouped within participants (level 2). Models will include treatment, baseline score, time-by-treatment interaction and minimisation factors as fixed effects. Educational participation will be analysed as total days missed during the 3 year follow up using a Negative Binomial regression model, adjusting for treatment and minimisation factors as fixed effects. Degree of residual deformity will be analysed as Stulberg grade at 3 years follow up using an ordinal logistic regression model, adjusting for treatment and minimisation factors as fixed effects. The number and proportion of participants experiencing each type of complication will be summarised by treatment group. Heterogeneity by centre will be explored visually using forest plots and with a sensitivity analysis on the primary outcome where statistical models applied will also adjust for centre as a random effect.

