24 HEALTH ECONOMICS

There is an integrated economic evaluation in this study, this will be informed by the NICE Reference Case [40] and reported according to the Consolidated Health Economic Evaluation Reporting Standards (CHEERS) statement [41].

OPNonSTOP_Protocol_V2.0_27Aug2024.docx

The economic evaluation will be conducted from the perspective of the UK NHS and Personal Social Services. A participant's use of primary, secondary and community care services and medications will be collected using an electronic resource use questionnaire [42] at the timepoints listed in Table 9. The resource use questionnaire has been designed with particular note to the relevance of information and the complexity of the task. Unit costs will be applied to resource use using national reference sources.

Health states will be determined using the CHU-9D questionnaire, with utilities derived based on an age-specific valuation set QALYs will be calculated using an area under the curve approach. Missing data will be managed following best practice, and imputation will be considered to avoid the potential bias of complete case analysis. Costs and QALYs will be discounted at the recommended rate and adjusted for any baseline difference using regression models [43, 44].

The primary economic outcome will be the incremental cost-effectiveness ratio (ICER) expressed as the incremental cost per QALY gained. Uncertainty in costs and QALYs will be assessed using bootstrap credible intervals, with the probability of cost-effectiveness at different willingness to pay threshold values represented using cost-effectiveness acceptability curves.

From a broader socioeconomic perspective, out-of-pocket expenses and workdays missed by parents because of their child's condition, and time off school will be recorded and reported.

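### The school-absence model leaves out baseline mobility and pain, which are collected on every child, and may lose some precision by doing so

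*Protocol*

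**What the plan says.** **School absence.** Table 7 (section 9.4), Table 9 (section 17.1) and Appendix 2 agree that it is collected at 3, 6, 9, 12, 18, 24, 30 and 36 months. The item "Participation in Education" is in every follow-up list of Appendix 2 and not in the baseline list. Section 23.3.2 takes the sum of days missed over three years and compares it "using a Negative Binomial regression model, adjusting for treatment and minimisation factors as fixed effects". The minimisation factors are age group, sex and lateral pillar collapse (section 15.3).

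**Other outcomes.** The primary model in section 23.3.1 includes the baseline score. So do the repeated-measures models in section 23.3.2 for mobility over time, pain, CHU-9D and family relationships.

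**Baseline data.** Table 9 and Appendix 2 schedule PROMIS Mobility, Wong-Baker pain, CHU-9D and Family Relationships at baseline.

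**Resource use and costs.** Table 9 and Appendix 2 start the resource-use questionnaire at 3 months. The cost-effectiveness row of Table 7 gives its time points as "Baseline (CHU-9D only), 6, 9, 12, 18, 24, 30 and 36 months post randomisation", which leaves out 3 months. Section 24 states: "Costs and QALYs will be discounted at the recommended rate and adjusted for any baseline difference using regression models".

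**The concern.** A total of days missed over three years will vary widely between children. Section 8.3 reports that the disease has a marked effect on school attendance, so a child's function and pain at entry are natural candidates as predictors of later absence. Where an outcome has its own baseline value, the protocol adjusts for it. School absence has none, and no substitute is used, although suitable scores are already held. If those scores predict absence beyond the three minimisation factors, omitting them widens the confidence interval for the rate ratio for no saving in data collection. It also leaves any chance imbalance in mobility or pain unadjusted for this outcome.

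The protocol itself names the covariates of this model, so this is a choice it has made and not a detail left to the SAP.

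**Working it through.** **1. The plan's own figure.** Section 23.2 states: "172 participants providing data on the PROMIS Mobility Score for children at three years post randomisation (86 in each group) will provide 90% power". The inputs behind it are a mean difference of 5, an SD of 10 and a two-sided t-test at the 5% level. The total is then "inflated to 216 participants (108 per arm) to allow for 20% attrition".

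- Normal approximation: n per arm = 2(1.960 + 1.282)² × 10²/5² = 84.1, so 85.
- Exact t-test: 85.03, so 86 per arm; power at 86 is 0.903.
- Attrition: 172/0.80 = 215, rounded to 216 for equal arms.

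The figure reproduces. It concerns the primary outcome only. The protocol gives no precision figure for school absence.

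**2. Inputs for the precision check.**

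- From the protocol: 86 children per arm, assuming that absence totals are available for the same 172.
- Assumed, because the protocol does not give them: mean days missed μ of 20 to 80, negative binomial dispersion k of 0.5 to 1.0, and the strength of prediction. That strength means what the baseline scores add beyond age group, sex and collapse, since those are already in the model.

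Without the covariate, SE(log rate ratio) = √[(2/n)(1/μ + k)], with n = 86.

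**3. Strength as a share R² of the dispersion k.** With the covariate, SE = √[(2/n)(1/μ + k(1 − R²))]. For μ = 40, k = 1.0 the SE without the covariate is √[(2/86)(0.025 + 1.0)] = 0.1544.

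| R² (r) | SE with covariate | Reduction | Range over μ 20–80, k 0.5–1.0 |
|---|---|---|---|
| 0.04 (0.2) | 0.1514 | 2.0% | 1.8–2.0% |
| 0.09 (0.3) | 0.1475 | 4.5% | 4.2–4.5% |
| 0.16 (0.4) | 0.1418 | 8.1% | 7.6–8.2% |
| 0.25 (0.5) | 0.1343 | 13.0% | 12.1–13.2% |

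At r = 0.1 the gain is 1 − √0.99 = 0.5%.

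**4. Strength as a share s of the variance of the log rate.** Let k be the dispersion left once the covariate is in the model. For gamma heterogeneity the log-rate variance is ψ′(1/k), where ψ′ is the trigamma function: 0.645 at k = 0.5 and 1.645 at k = 1.0. A normally distributed score explaining share s has variance v = [s/(1 − s)] ψ′(1/k). Omitting it raises the dispersion to k* = (1 + k)eᵛ − 1. The reduction is 1 − √[(1/μ + k)/(1/μ + k*)]. With μ = 30:

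| s | k = 0.5: k*, reduction | k = 1.0: k*, reduction |
|---|---|---|
| 2% | 0.520, 1.8% | 1.068, 3.1% |
| 5% | 0.552, 4.5% | 1.181, 7.7% |
| 10% | 0.611, 9.1% | 1.401, 15.1% |

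Simulated data agree. With 172 children, mean 30 and dispersion near 1, the SD of the estimated log rate ratio fell from 0.173 to 0.163 (6%) at s = 5% and from 0.171 to 0.152 (11%) at s = 10%. These come from 300 runs each, so the second digit is uncertain.

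Steps 3 and 4 differ in how they define predictive strength, and neither is in error. Together they span roughly 1% to 15%.

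**5. What that means for the interval.** Take s = 5%, k = 1.0. The SE without the score is √[(2/86)(0.0333 + 1.181)] = 0.168, and with it √[(2/86)(0.0333 + 1.0)] = 0.155. Around a rate ratio of 1, the 95% interval goes from 0.72–1.39 to 0.74–1.36.

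**6. Resource-use time points.**

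| Place | First follow-up point |
|---|---|
| Table 7, cost-effectiveness row | 6 months |
| Table 9 | 3 months |
| Appendix 2 | 3 months |

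The same Table 7 row covers CHU-9D, yet the separate CHU-9D row of Table 7 does list 3 months.

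**The case against.** The strongest reply is that nothing here is invalid. Allocation is randomised, the outcome accrues entirely after randomisation, and a negative binomial model with treatment and the minimisation factors gives sound inference. That stands. Starting collection at the first follow-up is also normal for such a count and is no fault.

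A second reply is that section 23.3.2 follows a consistent rule: outcomes measured at baseline adjust for their own score, while school absence and Stulberg grade, which have no baseline counterpart in the plan, adjust for the minimisation factors. That is a fair description, but it is no reason to leave out a different baseline score that is already held.

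A third is that the gain is assumed. The protocol gives no mean, dispersion or correlation for school absence, and section 8.3 does not say that mobility or pain at entry predicts absence over three years. The model already adjusts for three factors that section 15.4 names as prognostic, so only the additional prediction counts. This also stands. A reader might infer that precision is certainly being discarded, or that the change is worth about a fifth more children. The latter needs an SE reduction near 10% (1/0.90² = 1.23); at r = 0.3 or less the gain in step 3 is under 5%.

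**Conclusion.** The point holds as a minor efficiency improvement to one secondary outcome. The school-absence model in section 23.3.2 omits baseline mobility and pain that the trial collects on every child. The planned analysis is unbiased. The possible gain is about 1% to 15% of the standard error of the log rate ratio, on assumed mean, dispersion and predictive strength, and it is negligible if the scores barely predict three-year absence beyond age, sex and collapse. The log link means that adding the scores does not change the rate ratio being estimated under randomisation, provided the treatment effect does not vary with them.

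A reader might go further and infer that, because no baseline resource use is scheduled, the cost adjustment in section 24 cannot be done. The protocol does not support that. Section 24 speaks of baseline differences in general and does not promise a baseline-cost term. Baseline CHU-9D, sex, deprivation index, disease stage, stiffness and collapse are all collected and can serve. Which of them enter the cost regression is detail for the statistical and health analysis plan announced in section 34.

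The Table 7 discrepancy over 3 months is a separate, factual inconsistency. Its consequence depends on the recall period of the questionnaire, which the protocol does not state. If the 6-month form looked back only 3 months, following Table 7 would miss the first quarter, in which Appendix 1 aims for the intervention to be delivered.

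**What to change.** - **Section 23.3.2:** state that the school-absence negative binomial model also includes baseline PROMIS Mobility and baseline Wong-Baker score as prespecified continuous covariates. This is a wording change. It uses data already scheduled and costs two model parameters. It should be made before any comparative data are seen.
- **Table 7, cost-effectiveness row:** reconcile its time points with Table 9, Appendix 2 and the CHU-9D row of Table 7, so that the 3-month collection is either listed everywhere or nowhere. This too is a wording change.

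No change is needed to section 24, the sample size or the baseline visit on account of this point.
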